SpO ₂	Peripheral Capillary Oxygen Saturation
TBL	Total Bilirubin
TEAE	Treatment-Emergent Adverse Event
ТТІ	Time to Intervention
ULN	Upper Limit of Normal
WBC	White Blood Cell Count

1. Introduction

The purpose of this Statistical Analysis Plan (SAP) is to provide details of the statistical analyses that have been outlined within the protocol amendment 1 for Blinatumomab study 20190014, dated **21 April 2022**. The scope of this plan includes the interim analysis, and the primary analysis.

2. Objectives, Endpoints and Hypotheses

2.1 Objectives and Endpoints

Objectives	Endpoints	
Primary		
• To determine the safety of outpatient blinatumomab administration, during the MDMP (defined as the first 3 days of cycle 1 and first 2 days of cycle 2 of outpatient blinatumomab infusion)	 Grade 3 and/or 4 CRS, NT or any adverse event (AE) requiring hospitalization (SAE) during MDMP. 	
Secondary		
• To determine the time from first detection of grade 3 or 4 vital sign, or significant clinical change to therapeutic intervention (any measurable action taken by or performed on the subject due to onset of the clinical parameters described above) during the MDMP	• Time (in minutes) from first onset of fever, hypotension, hypoxia, other grade 3 or 4 vital sign including seizure or neurological change (grade 3-limiting self-care activities of daily living [ADL]) to therapeutic intervention.	
 Evaluate the safety and tolerability of blinatumomab administered exclusively as an outpatient 	 Treatment-emergent adverse events (TEAE) and adverse events of interest in particular CRS and NT. 	
• Evaluate the impact of complete outpatient blinatumomab treatment on patient-reported outcome (PRO), global health status (GHS), and quality of life (QoL).	 European Organisation for Research and Treatment of Cancer (EORTC) validated electronic version of QLQ-C30. 	
Estimate healthcare resource utilization associated with treatment-related AEs	 Treatment-related TEAEs that resulted in hospitalizations. Treatment-related TEAEs that resulted in surgeries. Treatment-related TEAEs that resulted in the use of concomitant medications. Treatment-related TEAEs that resulted in the use of device/procedure intervention. 	

ADL = activities of daily living; AE = adverse event; CG = caregiver; CRS = cytokine release syndrome; EMS = Emergency Medical Service; EORTC = European Organisation for Research and Treatment of Cancer; GHS = global health status; HCP = Health Care Provider; IV = intravenous; MDMP = mandatory device monitoring period; NT = neurotoxicity; PO = by mouth; PRO = patient-reported outcomes; QLQ-30 = Quality of Life of Cancer Patients; QoL = quality of life; SAE = serious adverse event; TEAE = treatment-emergent adverse event.

2.2 Hypotheses and/or Estimations

No formal hypotheses will be tested. For the primary and secondary objectives, analyses will be descriptive and include estimations.

3. Study Overview

3.1 Study Design

This study **aims** to determine the safety and feasibility of complete outpatient blinatumomab administration for subjects with MRD of B-precursor ALL. The study will use the CWHMS that is comprised of **CH** wearable **device** worn on the **subject's** upper arm, **an** axillary temperature patch, a blood pressure cuff, a Wi-fi hub, tablet, **a** mobile phone **provisioned to the HCP**, and a platform will also be used to monitor subjects' vital signs while they are at home.

This study will include remote monitoring using CWHMS to measure vital signs and mobile electronic devices (tablet) to electronically communicate these vital signs with the HCP.

The use of a Wi-Fi **and cellular** enabled platform for the transfer of data and communication between subject and HCP, to identify subjects at risk of developing grade 3 or 4 CRS, NT, or other SAEs requiring hospitalization during the MDMP. This subject group may require immediate escalation of care and/or hospitalization once the digital monitoring system identifies changes.

Design

During screening, subjects and caregivers will be trained on the CWHMS and assessed for compliance (Table 1, panel 1). **Once enrolled,** Subjects will receive 2 **complete** cycles of blinatumomab completely in the outpatient setting in accordance with the monitoring and intervention guidelines (Table 1, panels 2 and 3).

After the end of cycle 2 clinical assessment visit, some subjects may continue to receive 2 additional (optional) cycles of outpatient blinatumomab. There will be no CWHMS outpatient monitoring during the optional cycles 3 and 4. For the purpose of this study, the MDMP is defined as the first 3 days of cycle 1 (72 hours) and the first 2 days of cycle 2 (48 hours) of blinatumomab infusion for subjects with MRD of B-precursor ALL.

The end of study visit will occur 30 days (\pm 3 days) after the last dose of blinatumomab is **administered (Figure 1)**.

During the MDMP, the CWHMS will measure vital signs. These vital signs include pulse rate, respiratory rate, and axillary temperature. The CWHMS will measure respiratory rate (RR) intermittently (sampling every 30 seconds). The subjects will take intermittent blood pressure (BP) measurements (using a subject-usable BP device) every 3 hours during the MDMP. The schedule for BP measurements may be extended by HCP (up to but not exceeding every 6 hours) after the first 24 hours of MDMP. The BP device will be provided and will directly transmit the BP reading via the monitoring platform to the CH Patients Application on the study provisioned mobile phone.

Threshold vital sign values will be established, and an immediate alert will be generated and transmitted to the HCP device once the preset threshold values are surpassed and sustained for at least 10 minutes (Table 1). Except for blood pressure, an alert will be triggered within 1 minute upon being received.

The overall study design is described by a study schema in Figure 1. The endpoints are defined in Section 2.1. There will be no outpatient digital monitoring during the optional cycles 3 and 4.

Figure 1. Study Schema

ALL = acute lymphoblatic leukemia; CIVI = Continuous IV infusion; CR = Complete Remission; MRD = Minimal/Measurable Residual Disea

Screening must be completed within 21 days of enrollment. Eligibility CR and MRD bone marrow assessments must be no more than 14 days prior to informed consent. Screening to establish digital health monitoring baseline must be completed within 7 days of enrollment. Digital Health monitoring devices will be tested for a minimum of 24 hours. a End of Cycle 2 clinical assessment to be performed on day 29 pf cycle 2.

^c End of Study to be conducted 30 (+3 days) after last dose of blinatumomab

All MRD assessments per institutional standard of care procedures. No central MRD testing will be required Subjects can be transplanted at any time according to institutional guidelines and Standard of Care.

3.2 Sample Size

The planned enrollment for this study is **approximately** 45 **patients**. The sample size is based on feasibility rather than on statistical considerations. Given a true probability of a primary endpoint event of 38%, the expected 95% upper confidence limit with 45 subjects would be 53.5%. The 38% probability is based on the SAE rate in first 3 days of cycle 1 and first 2 days of cycle 2 from the previous MRD study (BLAST). Based on these assumptions, we expect to observe approximately 17 subjects who will experience

the primary endpoint which should provide an initial indication of the timeliness of the therapeutic intervention when outpatient blinatumomab is administered in conjunction with remote digital monitoring.

4. Covariates and Subgroups

4.1 Planned Covariates

No covariate analysis is planned for the study.

4.2 Subgroups

Due to small sample size, subgroup analysis will not be performed.

5. Definitions

Age at Enrollment:

Subject age at enrollment will be collected in years in the clinical database.

Adverse Event During the MDMP

Adverse event during the MDMP is defined as an adverse event that started within 72 hours after the first dose of blinatumomab in cycle 1 and within 48 hours after the first dose of blinatumomab in cycle 2.

For adverse events with missing start time, the adverse event during the MDMP is defined as an adverse event that started within 3 days after the first dose date of blinatumomab in cycle 1 and within 2 days after the first dose date of blinatumomab in cycle 2.

Baseline

The baseline value will be defined as the value measured on day 1 of the first cycle before start of the first infusion of blinatumomab. If a cycle 1 day 1 value is not available, the latest value before the day 1 of the start of blinatumomab infusion may be used.

Cumulative Dose of Blinatumomab

The cumulative dose in μg is defined as the following with summation over infusions:

 \sum Duration of infusion [days] for each dose received × dose received [μ g/day].

Cumulative dose will be calculated within a cycle and across all cycles.

Duration of Therapy

For each infusion episode within a cycle, the duration of exposure will be calculated by subtracting the start date and time from the stop date and time. If either a start or stop time is missing, only the date portion will be used in calculating the duration of a specific

infusion. For each cycle, the duration will be the sum of the individual infusion durations within that cycle. For the entire study, the duration will be the sum of the durations across cycles. The duration will be rounded to the nearest day.

End of Study

The end of study date is defined as the date when the last subject across all sites is assessed or receives an intervention for evaluation in the study (i.e. last subject last visit).

End of Study Visit

The end of study visit will occur 30 days (\Box 3 days) after the last dose of blinatumomab is given. The end of study visit will occur after cycle 3 or 4 for subjects who chose these optional cycles. End of study visit date for each subject will be recorded on the End of Study CRF page.

Enrollment Date

The date of enrollment is the date the subject has met all the eligibility criteria. This date will be documented in Subject Enrollment case report form (CRF) by investigator.

EORTC Quality of Life Questionnaire (EORTC QLQ-C30)

The EORTC QLQ-C30 is a 30-item guestionnaire that assesses the health related quality of life of cancer subjects participating in clinical trials (see Table B.1). The EORTC QLQ-C30 forms a global health status (GHS)/guality of life (QoL) scale, 5 functional domains (physical, role, emotional, cognitive and social), and 9 symptom domains (fatigue, nausea and vomiting, pain, dyspnea, insomnia, appetite loss, constipation, diarrhea, and financial difficulties). No question occurs in more than one scale (see Table B.1 & B.2). The score for each scale will be derived using the sum of the non-missing responses from all the associated questions and the corresponding range, assuming the number of items with non-missing scores meets the minimum requirement as specified in Table B.2, otherwise this scale score will be scored as missing. Range for a scale/item is defined as the maximum value – minimum value given in the guestionnaire (see Table B.2). All of the scales/items measures will get mapped to a common range from 0 to 100. A high scale score represents a higher response level. Thus, a high score for the global health status/QoL scale represents a high QoL, a high score for a functional scale represents a high/healthy level of functioning; but a high score for a symptom scale/item represents a high level of

symptomatology/problems. The score will be calculated as follows (Aaronson et al 1993):

Raw score = RS = $(Item_1 + Item_2 + ... + Item_n)/n$ (i.e., average)

Score transformed to 0-100 scale:

- Global health status/QoL score = {(RS-1)/score range} × 100
- Functional scales score = {1 (RS-1)/score range} × 100
- Symptom scales\items score = {(RS-1)/score range} × 100

The score range is the difference between the maximum possible value of the RS and minimum possible value.

If at least half of the items from the scale have been answered, then the missing items are imputed based on the average of those items that are answered. The single-item measures are not eligible for imputation. For scales missing more than half the items or for the single-item measures, the score will be set to missing (Aaronson et al 1993).

Mandatory Device Monitoring Period (MDMP)

For the purpose of this study, the mandatory device monitoring period (MDMP) is defined as the first three days of cycle 1 (72 hours) and the first 2 days of cycle 2 (48 hours) of blinatumomab infusion.

Therapeutic Intervention (TI)

Therapeutic intervention is any measurable action taken by the subject or performed on the subject as a result of the onset of the clinical parameters described. Such actions may include:

- Advised subject to go to hospital/ER immediately
- Advised subject to call 911 immediately
- Advised to suspend blinatumomab
- Advised to take antipyretic (e.g. acetaminophen)
- Advised subject to take dexamethasone
- Advised to suspend blinatumomab and take antipyretic
- Advised to suspend blinatumomab and take dexamethasone
- Advised to take other medication

• Other (if Other, describe the intervention)

Time to Therapeutic Intervention (TTI)

Time to therapeutic intervention is the time between the delivery of the device alert or unscheduled contact with HCP by subject/CG to report a change to the time of initiation of the therapeutic intervention.

TTI will be calculated as duration (in minutes) from time of the device alert (alarm triggered) to the time of initiation of the therapeutic intervention (i.e. when HCP silenced the alarm and advised an intervention).

If there is a case where the alarm is triggered, and the HCP advised an intervention, but event is not resolved and subject/CG presses the alarm again then that would be considered as a separate event (as alarm ID will be different) to calculate TTI.

TTI will be calculated for all the valid alarm triggers which leads to an intervention. If the calculated TTI is considered incongruous (i.e. more than 15min.) then a query will be entered in DIIR log.

All the scenarios defined below will be considered as invalid for calculation of TTI:

- If no intervention is required (e.g. technical issues) corresponding to an alarm.
- If intervention time is prior to the time of device alert (alarm triggered).

Treatment-emergent Adverse Event

Treatment-emergent Adverse Event is defined as adverse events starting on or after first dose of blinatumomab as determined by "Did event start before first dose of investigational product" equal to "No" or missing on the Events eCRF and up to the end of study visit.

Any TEAE reported as serious will be considered as treatment-emergent serious adverse events (SAEs). Any AE or SAE reported post end of study visit by site will not be considered as treatment-emergent.

6. Analysis Sets

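### The SAP defines time to therapeutic intervention as alert or contact to action, calculates it as alarm to HCP advice, and does not list the departure from the protocol

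*SAP*

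**What the plan says.** TTI is the key secondary endpoint. Footnote a in Protocol Section 3 (repeated in the Synopsis) starts it at the device alert or at unscheduled contact with the HCP, and stops it when the intervention begins. An intervention is an action by or on the subject. The footnote's examples include one form of advice, to call emergency medical services (EMS) or 911. The others are acts, such as stopping the infusion or taking a medication.

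SAP Section 5 repeats this. "Therapeutic intervention is any measurable action taken by the subject or performed on the subject", it says, and TTI starts at "the delivery of the device alert or unscheduled contact with HCP by subject/CG to report a change". The objective in SAP 2.1 uses the same action wording: "any measurable action taken by or performed on the subject due to onset of the clinical parameters described above".

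The calculation paragraph in SAP Section 5 differs. "TTI will be calculated as duration (in minutes) from time of the device alert (alarm triggered"), it says, and the interval ends at "the time of initiation of the therapeutic intervention (i.e. when HCP silenced the alarm and advised an intervention"). Every named entry in the SAP's list of interventions is worded as advice, for example "Advised to suspend blinatumomab and take dexamethasone". Only the entry for other interventions is left open.

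SAP 9.6.1 analyses TTI as defined in Section 5, with a continuous summary of valid, non-missing values. SAP Section 10 records changes to Sections 2.1 and 8.3 only.

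**The concern.** Two adjacent paragraphs of one SAP section give different start and stop points for the same variable, and the one that drives the programming is the one that departs from the protocol. Protocol 9.2 and SAP 3.2 both say that the expected events should give a first indication of how timely the intervention is under remote monitoring. If the calculation is followed, the number reported under the TTI label shows how quickly the HCP gave advice. That is useful to know, but it is not how quickly the intervention began. In a descriptive study the meaning of the result rests on its definition, so an undisclosed difference matters even though nothing is tested.

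**Working it through.** The plan states no figure for TTI, so this is a comparison of text. The nearest figure is the expected number of subjects with a primary event: 45 × 0.38 = 17.1, which agrees with the stated 17. It does not depend on the TTI definition. It also counts subjects with a primary event, whereas the SAP calculates TTI per alarm, so it cannot be used to size the effect.

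| Source | Start | Stop |
|---|---|---|
| Protocol Section 3, footnote a | Device alert or unscheduled contact | Start of the intervention |
| SAP Section 5, definition | Device alert or unscheduled contact | Start of the intervention |
| SAP Section 5, calculation | Device alarm only | HCP acknowledges the alarm and advises |
| Protocol Section 3 and SAP 2.1, endpoint; Protocol 9.4.2.3.1 | First onset | Intervention |
| Protocol Section 3 and SAP 2.1, objective | First detection | Intervention |

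**Stop time.** Let A be the alarm, V the advice and B the start of the action. The calculation gives V − A and the definition gives B − A, so they differ by B − V. For advice to call EMS or 911, the protocol counts the advice as the intervention, so B = V and the two agree. For an intervention that consists of stopping the infusion or taking a medication after being told to, the calculation leaves out B − V. No passage gives a value for it.

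**Start time.** Pressing the tablet button for feeling unwell raises an alarm (Protocol Synopsis, Design), and patient message is an alarm reason in SAP 9.6.1, so that route is covered. The Synopsis also gives subjects direct phone and video contact with the HCP. Such contact without an alarm is in the definition but has no start time in the calculation.

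**First onset.** This is not interchangeable with the alert. Leaving blood pressure aside, Table 1-1 requires a vital sign to stay past its threshold for at least 10 minutes before an alert.

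**Unanswered signals.** Under the Synopsis, a subject or caregiver who has no HCP reply 10 minutes after the first signal calls EMS. That path contains no HCP advice, so the stated stop time does not fit it. Protocol 9.4.2.3.1 allows a censoring approach such as Kaplan-Meier when events prevent an intervention. SAP 9.6.1 does not carry this over. Its alarm and intervention tables do not separate alarms that needed no intervention from alarms that had no reply.

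**Disclosure.** SAP Section 10 mentions endpoint wording, resource utilization and the replacement rule. It mentions neither TTI nor the dropped censoring option.

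**The case against.** The best defence is that the calculation sentence only makes the definition workable, because the platform records when an alarm is raised and acknowledged, not when a tablet is swallowed. The protocol's list of interventions is also open, and it accepts advice as an intervention in one case. Part of this stands. For advice to call EMS or 911 there is no conflict, and for medications the advice time may be the only clock time available. But both documents govern the list with the phrase about action by or on the subject, and a proxy should be named and disclosed as one.

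The start conflict is also narrow. Button presses are covered, and the documents do not show what the vendor data or case report forms hold for other contacts. The point is therefore about the SAP's wording, not about what was recorded.

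A reader might infer that the analysis can never reveal an unanswered signal. The documents do not support that. The HCP's alarm repeats every 5 minutes until answered, so a late reply can still be timed, and a TTI above 15 minutes is queried. SAP 9.6.1 tabulates all alarms and interventions, and the entry for other interventions is open. An EMS call after silence is neither of the two invalid cases, "If no intervention is required (e.g. technical issues) corresponding to an alarm" and "If intervention time is prior to the time of device alert (alarm triggered"). What remains is that the stated stop time does not fit that call.

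A reader might also infer from Protocol 6.5 that infusion interruptions of an hour or less go unrecorded. That section requires documentation of longer interruptions, directly after a passage on technical or logistic ones. It does not say that shorter or adverse-event-driven ones are left out, and SAP Section 5 uses start and stop times for each infusion episode.

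Finally, the SAP prints its stop rule openly, so someone who reads Section 5 is not misled. Someone who sees only a table labelled TTI may be.

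**Conclusion.** The point holds as a contradiction within SAP Section 5 and an unlisted departure from the protocol. As calculated, the key secondary endpoint is a time to HCP advice for every intervention other than advice to call EMS or 911. Alarm-free contact has no start time, an EMS call after silence has no fitting stop time, and first onset is left unreconciled.

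The size cannot be determined from the documents. A reader might infer that the reported TTI will be too short by some calculable amount. For a single alarm where the action follows the advice, the calculated interval is shorter by B − V, but the documents do not give that lag. Nor do they say how many contacts come without an alarm or how many signals go unanswered, and including those cases could move the summary either way. The primary endpoint is unaffected, no hypothesis is tested, and the planned sample size and its stated figures stay as they are. It is worth correcting because the change is cheap and the endpoint's meaning depends on it.

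**What to change.** Amend SAP Sections 5, 9.6.1 and 10 before database lock:

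1. State one start for TTI that includes unscheduled contact without an alarm, and reconcile it with the first-onset and first-detection wording.
2. Label the alert-to-advice interval *time to HCP response*. Report time to actual initiation only where a clock time was recorded, for example infusion stop times, which SAP Section 5 already uses for duration of therapy. Disclose that Protocol 6.6.2 collects concomitant therapy by date only.
3. Count alarms with no HCP response separately from alarms where no intervention was required. Use the EMS call time as the stop where it was recorded, and otherwise censor as Protocol 9.4.2.3.1 allows.
4. List the departure from the protocol in SAP Section 10.

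The cost is SAP wording and some programming, mostly on alarm records that the SAP already uses. Some contact, EMS-call and action times may not be recoverable, time to actual initiation may be available for only some intervention types, and TTI may look less favourable.

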ADL = activities of daily living; AE = adverse event; CG = caregiver; CRS = cytokine release syndrome; EMS = Emergency Medical Service; EORTC = European Organisation for Research and Treatment of Cancer; GHS = global health status; HCP = Health Care Provider; IV = intravenous; MDMP = mandatory device monitoring period; NT = neurotoxicity; PO = by mouth; PRO = patient reported outcomes; QLQ-30 = Quality of Life of Cancer Patients; QoL = quality of life; SAE = serious adverse event; TEAE = treatment-emergent adverse event.

^a Therapeutic intervention is any measurable action taken by the subject or performed on the subject as a result of the onset of the clinical parameters described. Such actions may include: Advice from HCP to immediately call EMS or dial 911, discontinuation of the blinatumomab infusion, subject taking an oral medication, subject receiving a medication or intervention by any emergency or hospital medical services, intervention such as administering any medication (IV or PO or PR) or IV fluids or oxygen etc. Time to therapeutic intervention (TTI) is the measured time between the delivery of the device alert or unscheduled contact with HCP by subject/CG to report a change to the time of initiation of the therapeutic intervention as defined.

Background and Rationale

This study **aims** to determine the safety and feasibility of complete outpatient blinatumomab administration. Blinatumomab is a novel bispecific T-cell engaging (BiTE) single-chain antibody construct that links CD3+ T lymphocytes with CD19+ B cells. This may result in a significant degree of T cell-mediated immune activation in subjects, which has correlated with efficacy but also with notable toxicity. The result is a heightened T-cell activation and release of pro inflammatory cytokines and the clinical manifestation of CRS. Along with CRS, another potentially severe toxicity observed is NT. Subjects may show signs of encephalopathy with varying degrees of severity and may experience delirium, aphasia, lethargy, difficulty concentrating, agitation, tremor, seizures, and, rarely, cerebral edema.

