Subjects will be trained to resend the "I don't feel well" signal if no response from the HCP is received in 5 minutes. If there is still no response after another 5 minutes, 10 minutes total from the initial alarm, then the subject or caregiver is to call Emergency Medical Service (EMS) or dial 911 immediately. Likewise, if the HCP responds to any alarm generated from the subject and the subject or caregiver does not answer within 10 minutes, then the HCP will make 1 attempt to call the subject's personal phone. If the

Date: 21 April 2022 Page 14 of 108

subject or caregiver is still not reachable, the HCP will have EMS dispatched to the subject's location immediately.

The **study provisioned mobile phone** is configured so that a loud audible alarm is made and repeated every 5 minutes until the HCP responds or if no data is transferred for 15 minutes.

The HCP will then use the compendium of vital sign's absolute value and/or deviation from baseline (provided by the CWHMS) and the subject's clinical status (provided by direct subject/caregiver telephone and video contact), to make decisions on urgency of response, appropriate intervention and subject disposition.

During MDMP, any device malfunction that results in lack of data transmission (eg, from the CH wearable device, axillary temperature patch) for 15 minutes will generate an alarm to the HCP. The HCP will contact the patient immediately via the video calling functionality to assess the patient's safety, clinical status, and any specific circumstances associated with the device malfunction (eg, device inadvertently dislodged, low battery charge, intermittent loss of signal transmission etc). If the HCP has any concern of patient safety, HCP will advise the patient to immediately go to the hospital.

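### The time-to-intervention clock stops only at advice from the healthcare provider, so an unanswered patient signal that ends in a subject's or caregiver's emergency call is mistimed or missing, and unanswered signals are not counted

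*SAP*

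**What the plan says.** SAP Section 5 defines an intervention broadly: "Therapeutic intervention is any measurable action taken by the subject or performed on the subject". Of the nine listed examples, eight are things the HCP advised; the ninth is an open category, Other. TTI is first described as running from a device alert, or an unscheduled contact with the HCP, to initiation of the intervention. The calculation sentence then starts the clock at the alert and stops it at the "time of initiation of the therapeutic intervention (i.e. when HCP silenced the alarm and advised an intervention".

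Footnote a to the protocol's objectives table (Sections 1.1 and 3) also takes the broad view. It includes "subject receiving a medication or intervention by any emergency or hospital medical services", as well as a subject taking oral medication and stopping of the infusion.

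The protocol Synopsis (Section 1.1, Design) sets two routes to EMS on which nobody has been advised:

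- **Route 1, the HCP does not answer.** The subject resends the signal at 5 minutes. With no answer by 10 minutes, "then the subject or caregiver is to call Emergency Medical Service (EMS) or dial 911 immediately".
- **Route 2, the subject does not answer.** If the subject or caregiver "does not answer within 10 minutes, then the HCP will make 1 attempt to call" the subject's own phone. If the "subject or caregiver is still not reachable, the HCP will have EMS dispatched".

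Three further SAP rules matter:

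- Section 9.6.1 summarizes only non-missing, valid TTI, and Section 8.3 in general leaves missing data missing.
- Long values are checked: "If the calculated TTI is considered incongruous (i.e. more than 15min.) then a query will be entered in DIIR log".
- After HCP advice has not resolved an event, if the "subject/CG presses the alarm again then that would be considered as a separate event (as alarm ID will be different").

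**The concern.** A home-monitoring feasibility study needs to show what happens when the monitoring chain fails. Route 1 is the protocol's safeguard against an HCP who does not respond. On that route the stopping condition in the SAP calculation has not occurred when the caregiver acts. The event can be entered as an intervention under Other and still have no TTI, or it can take the time of an HCP contact that came after EMS was called.

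Section 9.6.1 tabulates alarms by reason and interventions by type, but not signals the HCP left unanswered. A reader of the TTI table could therefore see only the occasions on which the HCP responded. Protocol Section 9.2 and SAP Section 3.2 say that the expected events should give an initial indication of timeliness, so this table carries a stated purpose of the study.

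**Working it through.** **The plan's own figure.** The sample-size text gives 45 subjects, a 38% event rate, about 17 events and an expected upper limit of 53.5%. Events: 45 × 0.38 = 17.1. The two-sided 95% Clopper-Pearson upper limit, averaged over Binomial(45, 0.38), is 53.52%; at 17 events it is 53.46%. The figure reproduces. The present point does not depend on it, because TTI is counted per alarm and the documents give no alarm or EMS counts.

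**Route 1.** Let EMS be called c minutes after the first signal. The broad definition gives TTI = c.

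- Following the Synopsis timing, c = 10.
- A call can come sooner. The Synopsis trains subjects to call EMS for any concern or any delay in reaching the HCP, and Table 1-1, Panel 3, allows direct contact. Take c = 3 as an example.
- Under the calculation sentence, TTI is missing if no HCP advice follows. If an HCP contact with advice follows at, say, 20 minutes, TTI is 20.
- The 15-minute query would flag the 20. It would not flag a later contact at 15 minutes or less, and it cannot flag a value that was never calculated.

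**Route 2.** Let the HCP respond at r minutes (assumed 1, 3 or 5) and wait the 10 minutes. Dispatch is then at r + 10 or later: 11, 13 or 15 minutes or more. If the HCP silences the alarm on responding (an assumption) and that is taken as the stop, TTI is 1, 3 or 5. The SAP does not say which applies.

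**Resent signal.** The SAP makes a repeat press a separate event only where HCP advice came first. It is silent on a signal resent at 5 minutes because nobody answered. If the HCP answers at t minutes, TTI could be t, t - 5, or the mean of the two if both count:

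| Answer at t | From first press | From resend | Mean if both count |
|---|---|---|---|
| 6 | 6 | 1 | 3.5 |
| 7 | 7 | 2 | 4.5 |
| 9 | 9 | 4 | 6.5 |

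**Effect on the mean.** Assume N answered TTIs averaging 5 minutes and k missing route 1 events with EMS called at c. With those events included, the mean is (5N + ck)/(N + k).

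| N | k | c | Mean | Change |
|---|---|---|---|---|
| 20 | 1 | 10 | 110/21 = 5.24 | +0.24 |
| 20 | 3 | 10 | 130/23 = 5.65 | +0.65 |
| 100 | 1 | 10 | 510/101 = 5.05 | +0.05 |
| 100 | 3 | 10 | 530/103 = 5.15 | +0.15 |
| 20 | 3 | 3 | 109/23 = 4.74 | -0.26 |
| 100 | 1 | 3 | 503/101 = 4.98 | -0.02 |

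N, k, c and the 5-minute mean are assumptions chosen to show scale; they are not bounds.

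**The case against.** The strongest reply is that this is a wording conflict within one definition. The general TTI sentence runs to initiation of the intervention, a caregiver's emergency call fits the broad definition, Other is available, and EMS events are not among the scenarios listed as invalid. A sensible programmer could time them. On route 2 the HCP does act, so a dispatch time can be entered. Route 1 concerns the patient signal, which appears to be one of seven alarm reasons. The HCP carries the phone throughout monitoring, its alarm repeats every 5 minutes, and triage nurses are available to sites, so non-response should be uncommon. The endpoint is descriptive, and an intervention without a TTI could be inferred by comparing the counts in Section 9.6.1.

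Most of this stands, and it limits the point. It removes any claim that route 2 has no stop time, or that EMS events are excluded by rule. It does not remove route 1. The calculation sentence is the operative rule and it narrows the general one; Other supplies a category but no time. Comparing counts would not separate an unanswered signal from any other missing TTI.

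A reader might also infer that dropping EMS events must make TTI look shorter than it was, on the view that they all took at least 10 minutes. The documents do not support that, because EMS may be called earlier. Nor do they support an effect on the primary endpoint: a hospitalization for an adverse event during the monitoring period counts there whatever its TTI.

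**Conclusion.** The point holds in a limited form. Applied literally, the stop rule mistimes or drops route 1 events, and the plan does not report how often the HCP failed to answer. For route 2 and for resent signals the rule is ambiguous. The effect on mean TTI is probably small and can go either way: -0.26 to +0.65 minutes in the cases worked here, all on assumed inputs. The frequency is unknown. The real loss is visibility of HCP non-response in the key secondary result, and that justifies a clarification before database lock.

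The protocol's option of a Kaplan-Meier approach where an event prevents an intervention (Section 9.4.2.3.1) is not carried into the SAP. It would not close this gap, because on route 1 an intervention did occur; what is missing is a rule for timing it.

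**What to change.** In SAP Section 5, replace the calculation sentence with:

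> TTI (minutes) runs from the first device alert, patient signal or unscheduled contact with the HCP for the event to the earliest of: HCP advice to act; a self-initiated action by the subject or caregiver that the protocol counts (EMS or 911 call, medication taken, infusion stopped); EMS dispatch by the HCP; first treatment by EMS or hospital. A signal resent before any HCP response belongs to the same event and does not restart the clock.

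In Section 9.6.1, add:

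> Report the number and percent of patient signals with no HCP response within 10 minutes, and the number of interventions without a TTI.

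The protocol's instruction to call EMS should stay as it is.

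The cost is two SAP edits before database lock and an EMS call or dispatch time recorded for the few affected events. Sites will need to be told to collect that time, and a time recalled by a caregiver may be approximate. The count of unanswered signals is a new output that neither document now promises, but it does not depend on caregiver recall of the EMS call time. No procedure or subject is added.
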